12 WITHDRAWAL FROM STUDY

Every reasonable effort should be made to maintain protocol compliance and participation in the study. Should a subject withdraw or be prematurely terminated from the study for any reason, the reason for early study withdrawal will be recorded. If withdrawal is the result of a serious adverse reaction, the subject will be followed until the condition has resolved, as determined by the Investigator.

The Investigator or Sponsor may withdraw any subject at any time for medical reasons or for administrative reasons (ie, subjects unable or unwilling to comply with the protocol). If so, the subject will be censored at time of withdrawal and, if possible, a final evaluation (end-of-study procedures) will be made. All treated subjects will be included in the safety analyses.

In the unlikely event the Sponsor or FDA should determine it is appropriate to terminate the study early, every effort will be made for transitioning subjects with minimal disruption to the subject and Investigator. The IRB/IEC will be notified of termination and reason(s). Procedures for follow-up of research subjects will be developed by the study physician in consultation with the Sponsor and IRB/IEC.

13 DATA MANAGEMENT

The standard procedures for handling and processing records will be followed as per GCP and the data management standard operating procedures of the contract research organization. A comprehensive Data Management Plan will be developed and approved by a representative of the Data Management contract research organization and the Sponsor.

13.1 Database Lock

The database will be locked in order to protect write access after the following preconditions are fulfilled:

- All data are entered in the database;
- All adverse events are recorded to the satisfaction of the Chief Medical Officer;
- All data queries have been resolved to the satisfaction of the Lead Biostatistician;
- All decisions have been made regarding all protocol violators and population exclusions;

- Written authorizations to lock the database are obtained from Clinical Data Management and the Chief Medical Officer.

14 ETHICAL CONSIDERATIONS

14.1 Ethical Conduct of the Study

The study will be conducted in accordance with US Title 21 CFR and the ICH E6 (R2) Good Clinical Practice: Integrated Addendum to ICH E6(R1) Guidance for Industry. The Declaration of Helsinki and its most recent updates (Fortaleza, Brazil; 2013) will be observed.

The Investigator will provide the Sponsor/designee with documentation of IRB/IEC approval of the protocol and the sample informed consent document before the study may begin at the investigative site. The IRB/IEC will review the protocol as required.

The Investigator will supply the following to the IRB/IEC:

- The current Investigator's Brochure and updates
- Study protocol and amendments
- Informed consent and assent document and updates
- Relevant curricula vitae
- Safety alerts
- Serious adverse reaction reports

The Investigator must provide the following documentation to the Sponsor or designee:

- The IRB/IEC original approval of the protocol and the informed consent, and re-approval of the study (annual or semi-annual, per IRB/IEC guidelines)
- The IRB/IEC approvals of any revisions to the informed consent document or amendments to the protocol
- All other documents that are required by local regulatory authorities

14.2 Regulatory Considerations

After reading the protocol, each Investigator/sub-Investigator will sign a protocol signature page and return a copy of the signed page to the Sponsor/designee, while maintaining the original at the site.

14.3 Protocol Amendments and Study Termination

The IRB/IEC must be informed and give approval for any amendments likely to affect the safety of the subjects or the conduct of the study.

The IRB/IEC must be advised in writing of the study's completion or early termination and a copy of the notification must be provided to the Sponsor.

14.4 Safety Monitoring

The Sponsor's Medical Monitor will monitor safety data throughout the course of the study. The Sponsor's Drug Safety Department, or their designee, will expedite to the regulatory authorities only the suspected adverse reactions that are product-related and unexpected in accordance with FDA 21 CFR 312, FDA Guidance on Safety Reporting Requirements for INDs, and the ICH E2A guideline.

14.5 Quality Control and Quality Assurance

By signing this protocol, the Sponsor agrees to be responsible for implementing and maintaining quality control and quality assurance systems with written standard operating procedures to ensure that the study is conducted and data are generated, documented, and reported in compliance with the protocol, accepted standards of GCPs, and all applicable federal, state, and local laws, rules and regulations relating to the conduct of the clinical study.

By signing this protocol, the Investigator agrees to conduct the study in an efficient and diligent manner and in conformance with this protocol, generally accepted standards of GCP, and all applicable federal, state, and local laws, rules and regulations relating to the conduct of the clinical study.

The Investigator also agrees to allow monitoring, audits, IRB/IEC review and regulatory agency inspection of study-related documents and procedures and provide for direct access to all study-related source data and documents. Investigators will be given notice before a quality assurance audit occurs.

The Investigator shall prepare and maintain complete and accurate study documentation in compliance with GCP standards and applicable federal, state, and local laws, rules and regulations, and promptly submit to the Sponsor all forms and reports required by this protocol following completion or termination of the clinical study or as otherwise required due to any agreement with the Sponsor.

15 GENERAL CONSIDERATIONS

15.1 Discontinuation of the Study

The Sponsor reserves the right to discontinue this study or the Investigator's participation in this study for safety or administrative reasons at any time.

## Revision History

Version	Date	Author	Summary of Changes
1.0	21 September 2021	[name]	First signed off version
2.0	12 April 2022	[name]	Globally, baseline is changed to Visit 1a. Section 7.2 a description for handling missing central lab tests or aberrant test results is provided. Section 7.3 is updated to be more specific for adaptation rule. Section 7.5 is updated for the primary and secondary endpoints derivation. Section 7.6 is added to include additional parameters of interest.
3.0	01 November 2022	[name]	See Section 2.3.

---

## LIST OF ABBREVIATIONS

AE	Adverse event
AKI	Acute kidney injury
ANCOVA	Analysis of Covariance
AUC	Area under the curve
Avg	Average
CABG	Coronary artery bypass graft
CI	Confidence interval
CMH	Cochran-Mantel-Haenszel $\chi^2$ test
CSR	Clinical study report
CysC	Cystatin C
eCRF	Electronic case report form
Exp	Exponential
FeS	Iron sucrose
GM	Geometric mean
GLSM	Geometric least squares mean
HO-1	Heme oxygenase-1
ICU	Intensive Care Unit
IL-10	Interleukin-10
IV	Intravenous
KDIGO	Kidney disease improving global outcomes
KIM-1	Kidney injury molecule-1
LLOQ	Lower limit of quantification
Log	Natural logarithm (base e)
LSM	Least Squares Mean
MAKE	Major adverse kidney events
MAKE30	Major Adverse Kidney Events through Day 30 post-cardiac surgery
MAKE90	Major Adverse Kidney Events through Day 90 post-cardiac surgery
MINP	Method of inverse normal p-values
MITT	Modified intent to treat
MMRM	Mixed model for repeated measures
NGAL	Neutrophil gelatinase-associated lipocalin
PostOp	Post cardiac surgery
PreOp	Immediately prior to the cardiac surgery
RBT-1	Stannous protoporphyrin and iron sucrose
SAE	Serious adverse event
SAP	Statistical analysis plan
SnPP	Stannous protoporphyrin
TEAE	Treatment-emergent adverse event

## 1 INTRODUCTION

The purpose of this statistical analysis plan (SAP) is to present the statistical methodology that will be used for the interim and final analyses of Renibus Therapeutics, Inc. protocol REN-004. This plan also provides a description of the tables, figures, and listings that will be included in the final statistical report. It is based on the protocol version 5 dated 25 August 2022 and on the annotated electronic case report form (eCRF). In case of differences in terms of descriptions or explanations between the SAP and the clinical protocol, the SAP will supersede the protocol. Any deviation to this SAP would be reported in the clinical study report (CSR).

[figure not shown]
## 2 STUDY DESCRIPTION

### 2.1 Study Design

This is a Phase 2, multicenter, double-blind, randomized, placebo-controlled study to evaluate the effect of RBT-1 on preconditioning response biomarkers in subjects who are at risk for acute kidney injury (AKI) following cardiac surgery. Eligible subjects will be randomized to receive a single dose of low dose RBT-1 (45 mg SnPP/240 mg FeS), high dose RBT-1 (90 mg SnPP/240 mg FeS), or placebo (normal saline) via intravenous (IV) infusion over a 120-minute period  $\geq 24$  but  $\leq 48$  hours prior to scheduled cardiac surgery.

All subjects will be assessed through Day 90 post-cardiac surgery. Subjects will be evaluated at Screening, 48 and/or 24 hours prior to surgery depending on the time of dosing, on Day 1 (day of surgery), and daily through Day 7 or Discharge if earlier, as well as on Days 30, 60, and 90, as described in the Event Schedule (see Appendix 1). Assessments include biomarkers of preconditioning response and tubular injury, urine output, incidence and severity of AKI, serum creatinine, days on ventilator, days in intensive care unit, hospital length of stay, readmission rate, and safety (physical examination, clinical laboratory assessment, vital signs, concomitant medications, and adverse events). Evaluations for major adverse kidney events (MAKE) (death, need for dialysis, and persistent decrease in kidney function) and safety will be performed through Day 90, as described in the Event Schedule (see Appendix 1).

The duration of the study will be approximately 90 days per subject. A schematic of the study design is presented below:

AKI = acute kidney injury, FeS = iron sucrose, h = hour, SnPP = stannous protoporphyrin

## 2.2 Study Objectives

The overall objective is to evaluate the effect of RBT-1 on preconditioning response biomarkers in subjects undergoing CABG and/or cardiac valve surgery.

The primary objective is to evaluate the efficacy of RBT-1 in generating a preconditioning response as measured by a composite of plasma biomarkers (plasma heme oxygenase-1 [HO-1], ferritin, and interleukin-10 [IL-10]) from Baseline (pre-dose) through Day 1 PreOp.

The secondary objectives are to evaluate the efficacy of RBT-1 on the following:

- Change in renal tubular injury biomarkers post-cardiac surgery through Day 3
- Reduction in urine output (documented adverse event [AE] of sustained reduction in urine output, oliguria, or anuria) post-cardiac surgery through Day 5
- Incidence of AKI (defined as a  $\geq 1.5X$  baseline, i.e., a 50% increase from baseline in serum creatinine; documented AE of sustained reduction in urine output, oliguria, or anuria; or initiation of dialysis) post-cardiac surgery through Day 5

The exploratory objectives are to evaluate the following:

- Severity of AKI post-cardiac surgery through Day 7
- Mean increase in serum creatinine post-cardiac surgery through Day 7 or until Discharge if prior to Day 7
- Occurrence of MAKE – death, need for dialysis, and persistent renal dysfunction ( $\geq 25\%$  decrease in estimated glomerular filtration rate [eGFR]) – post-cardiac surgery through Day 30 (MAKE30) and Day 90 (MAKE90) post-cardiac surgery
- Proportion of subjects experiencing MAKE30
- Proportion of subjects experiencing MAKE90
- Days on ventilator
- Days in intensive care unit (ICU)
- Hospital length of stay
- Readmission rate
- Changes in biomarkers of RBT-1 activity and/or kidney function

### **2.3 Changes from v2.0 to v3.0 Statistical Analysis Plan**

See APPENDIX B for detail.

## **3 ANALYSIS POPULATIONS**

The populations of analysis will be confirmed by the Sponsor prior to unblinding.

### **3.1 Intent-To-Treat (ITT) Population**

The ITT population will consist of all randomized subjects who were eligible for the study, received study drug, and had biomarker assessments performed at baseline (Visit 1a) and prior to surgery (Visit 1b and/or Day 1 PreOp). Subjects in the ITT population will be analyzed as randomized.

### **3.2 Modified Intent-To-Treat (MITT) Population**

The MITT population will consist of all randomized subjects who were eligible for the study, received study drug, underwent CABG and/or cardiac valve surgery without delay, and were evaluated through the end of index surgery hospitalization. Subjects in the MITT population will be analyzed as randomized.

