9.5.4 Dosage Preparation and Administration

Detailed instructions for dose preparation will be specified in the Pharmacy Manual.

Study drug (RBT-1 or placebo) will be administered via IV infusion over a 120-minute period ≥ 24 but ≤ 48 hours prior to scheduled cardiac surgery. Study drug administration may be performed in an outpatient setting.

Subjects will be observed for signs and symptoms of hypersensitivity during study drug administration and for at least 30 minutes after administration. Subjects should be

observed until they are deemed clinically stable. RBT-1 will only be administered when personnel and therapies are available for the treatment of any infusion-related reactions.

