11.2 Study Populations

The efficacy analyses will be conducted using the Intent-to-Treat population (all randomized subjects) and Per Protocol population (all randomized subjects who had no major protocol deviations). Safety analyses will be conducted using all subjects receiving any amount of study drug.

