## 7.5 Efficacy Analysis

Primary endpoint will be analysed using both the ITT and MITT populations. All other efficacy endpoints will be analyzed using the MITT population.

Surgery type and time on pump may be used as covariates in ANCOVA or MMRM, or as stratification factor in Cochran-Mantel-Haenszel (CMH)  $\chi^2$  test. When used as stratification factor, time on pump will be trichotomized by the approximate tertile ( $\leq 90$ ,  $>90$  to  $120$ ,  $>120$  minutes) of the distribution in the MITT population. Other variables (eg, AKI risk factor and investigator site) may also be considered as covariates or stratification factors. The decision for including/excluding these variables as covariates or stratification factors will be based on the blinded review prior to any unblinded analysis.

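### Every efficacy endpoint except the primary is analysed only in an MITT set that drops randomised, dosed subjects for delayed surgery or an index stay not followed to its end, so these comparisons can be biased in either direction

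*SAP*

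**What the plan says.** SAP 3.2 builds the MITT set from eligible, randomised, dosed subjects who "underwent CABG and/or cardiac valve surgery without delay, and were evaluated through the end of index surgery hospitalization", analysed as randomised. Neither the meaning of delay nor the status of a subject who dies in hospital is stated.

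SAP 7.5 then divides the endpoints. For the primary, "Primary endpoint will be analysed using both the ITT and MITT populations". For the rest, "All other efficacy endpoints will be analyzed using the MITT population". The table list in SAP 8 agrees: the tubular-injury, urine-reduction, AKI, creatinine, eGFR, MAKE and hospitalisation tables are all labelled MITT. No sensitivity analysis of these endpoints in a wider set is planned.

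Protocol 11.2 planned otherwise: "The efficacy analyses will be conducted using the Intent-to-Treat population (all randomized subjects"), together with a Per Protocol set. SAP 1 settles the conflict, since "the SAP will supersede the protocol". The SAP's own ITT set is narrower than the protocol's, because it requires that subjects "received study drug, and had biomarker assessments performed at baseline (Visit 1a) and prior to surgery (Visit 1b and/or Day 1 PreOp"). No efficacy analysis in the SAP therefore uses all randomised subjects.

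On timing, Protocol 9.5.4 says study drug "will be administered via IV infusion over a 120-minute period ≥ 24 but ≤ 48 hours prior to scheduled cardiac surgery". The one general safeguard on the sets is in SAP 3: "The populations of analysis will be confirmed by the Sponsor prior to unblinding".

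**The concern.** Surgery comes at least a day after the infusion. A reaction to the drug, or worsening illness, could postpone it, and a post-operative complication could end observation before discharge. Either event removes the subject from the only set used for the endpoints that bear on clinical relevance. If the chance of removal depends on treatment and is related to outcome, the arms that remain are no longer comparable.

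The completeness condition also discards outcomes that are already known. Tubular injury is measured through Day 3, and urine output and AKI through Day 5 (SAP 5.2.1 to 5.2.3). A subject with AKI recorded by Day 5 who is lost later in the same stay leaves the AKI analysis. Death is a component of MAKE (SAP 5.3.3). If an in-hospital death does not count as evaluation to the end of the stay, it would be removed from an endpoint meant to capture it.

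**Working it through.** **Inputs.** 42 per group, 1:1:1 (Protocol 4). Background post-operative AKI of about 30% (Protocol 6.1), which is not a rate under the SAP's own AKI definition. Fisher's exact test of each active arm against placebo (SAP 7.5.2.2 and 7.5.2.3), two-sided 0.05 (SAP 7.2). Secondary log composite: SD 0.51, difference 0.4 (SAP 7.1). Numbers excluded and their AKI risk are not in the documents and are assumptions throughout.

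**1. The plan's own figure.** SAP 7.1 states 40%, 69% and 86% power for the tubular-injury composite at 10, 20 and 30 per group. A two-sample t-test with SD 0.51 and difference 0.4 gives 38.2%, 67.6% and 84.8%. With ln 1.5 it gives 39.1%, 68.8% and 85.7%. The stated figures reproduce to within 2 points.

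**2. If exclusions are unrelated to treatment and outcome.** Only precision is lost. The same t calculation (difference 0.4) gives 94.4% power at 42 per group, 92.1% at 38 and 89.0% at 34.

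**3. If exclusions are selective.** Let true AKI be 30% in both arms and let one arm lose k subjects whose AKI risk is r:

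observed rate = (0.30 × 42 − k × r) / (42 − k)

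| k | r | Calculation | Observed rate | Shift (points) |
|---|---|---|---|---|
| 4 | 10% | (12.6 − 0.4)/38 | 32.1% | +2.1 |
| 4 | 30% | (12.6 − 1.2)/38 | 30.0% | 0 |
| 4 | 60% | (12.6 − 2.4)/38 | 26.8% | −3.2 |
| 4 | 80% | (12.6 − 3.2)/38 | 24.7% | −5.3 |
| 6 | 60% | (12.6 − 3.6)/36 | 25.0% | −5.0 |
| 6 | 80% | (12.6 − 4.8)/36 | 21.7% | −8.3 |

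The shift applies to whichever arm loses the subjects. High-risk losses from an active arm flatter it, and the same losses from placebo count against it. Low-risk losses reverse the sign.

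**4. Effect on the Fisher test.** By exact enumeration, the false-positive rate is 3.0% at 42 against 42 with no exclusion. With losses from one arm only it is about 4.5% (k=4, 60%), 6.3% (k=4, 80%) and 5.7% (k=6, 60%). If both arms lose 10%, with risk 60% among those lost from active and 30% among those lost from placebo, it is 3.8%. If both lose 15% it is 4.7%. If every excluded active subject had AKI, these last two become 7.9% and 16.0%.

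**5. Assumption-free bound.** If 4 of 42 are dropped from each arm and the MITT shows no difference, the difference in all 42 per arm could lie anywhere within ±4/42 = ±9.5 points.

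**6. Fragility.** AKI in 3/38 against 11/38 gives p = 0.036. Restore the 4 dropped per arm, with one AKI among the active subjects and none in placebo: 4/42 against 11/42 gives p = 0.085.

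**The case against.** **The scenarios are assumed.** Nothing in the documents links surgical delay to AKI risk, and a delay for scheduling reasons would cost only precision. The one-arm losses are chosen, and most of the moderate cases leave the Fisher test's false-positive rate near or below 5%. This stands. A reader might infer that the plan builds in a spurious 3 to 5 point benefit for RBT-1. The documents support neither that size nor that direction.

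**Eligibility.** A reader might count the eligibility requirement as a third post-randomisation exclusion. Mostly it is not: Protocol 9.7.2 re-confirms eligibility at Visit 1a among the procedures completed before dosing, with treatment assignment the last of them. Exclusions 6 and 7 cover the 24 hours before surgery and so can reach past dosing, but the point does not need them.

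**Safeguards.** The sets are confirmed before unblinding. Disposition, surgery received and population counts are reported by arm (SAP 7.4.1, 7.4.3), so it would be wrong to say exclusions go unreported; only the reason for each MITT exclusion is missing. AKI and death are also adverse events of interest in the Safety population (SAP 6.3, 7.6.1). Blinded confirmation prevents deliberate selection, but not bias from a treatment that itself affects delay or early exit. The safety tables are descriptive and do not replace the creatinine-based AKI, MAKE or length-of-stay comparisons.

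**Measurability.** A post-operative endpoint needs an operation, and a length of stay needs its end. The first justifies requiring surgery, not undelayed surgery. The second is a reason to censor hospital days, not to drop a known Day 5 AKI result.

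**Phase and priority.** The study is Phase 2 with a biomarker objective, the primary is also run in a set without these two conditions, and the gatekeeping covers only the primary. This limits the weight of the point but does not remove it.

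**Conclusion.** The point holds for two conditions: surgery without delay, and evaluation to the end of the index stay. Both follow dosing, both govern the sole analysis set for all non-primary efficacy endpoints, and no planned analysis would show whether they matter.

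The supported claim is that bias is possible, in either direction and of unknown size. As an illustration only, with 30% AKI in both arms and 42 per arm, the shift is about 3 to 5 points for 4 losses at 60% to 80% risk or 6 at 60%, all from one arm. It is 8.3 points at 6 losses and 80%, and zero when those lost have the average risk. It is worth correcting because the correction is cheap. It does not touch the primary result in the SAP's ITT set.

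Departing from the protocol's all-randomised set is not in itself a breach, since Protocol 11.3 defers the analysis details to the SAP and the SAP takes precedence.

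**What to change.** - Make the main set for post-operative efficacy endpoints all randomised, dosed subjects who had the index cardiac surgery, as randomised, whatever the delay or completeness of stay. Keep the present MITT as a sensitivity analysis, with delay defined.
- Count AKI, urine-output, dialysis and death events seen before loss. For subjects lost without an event before the endpoint window closes, state one rule and show a best-case and worst-case check.
- For ventilator, ICU and hospital days, censor incomplete stays in the Kaplan-Meier analysis that SAP 7.5.3.5 already allows, and state how in-hospital deaths are handled there and in the set definitions.
- Add the reason for each MITT exclusion, by arm, to the disposition and population counts already planned.

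The proposed set still conditions on having had surgery, which is also a post-dose event, so subjects whose surgery was cancelled should be shown by arm alongside it. It leaves untouched the separate restriction of MAKE to subjects with AKI through Day 5.

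The cost is SAP wording and one rerun of existing tables. Planned enrolment does not change. The downside is slight dilution from delayed-surgery or partly observed subjects.
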